- Suicidality, as assessed by the C-SSRS
- Change from baseline in cognition as measured by a composite test score comprised of the following CogState test battery tasks: Detection task (DET), Identification task (IDN), One-card Learning task (OCL), and One-back task (OBK)
- Change in severity of dissociative symptoms at each scheduled assessment, as measured by change from baseline in the CADSS total scores
- **Exploratory**
 - Change in anxiety at each scheduled assessment as measured by HAM-A total score
 - Effect of family history of alcohol abuse and GABRA2 on change in MADRS total score and percentage of patients who respond at each scheduled time point
 - Change from baseline in suicidal ideation at each scheduled assessment as measured by change from baseline in S-STS
- **Pharmacokinetics**
 - AZD6765 plasma concentration levels (for population pharmacokinetics [PK] analysis)
- **Pharmacogenetics**
 - Exploratory analysis of the genes involved in the PK, pharmacodynamics (PD), safety, and tolerability related to AZD6765iv treatment may be performed. The polymorphism of genes that may be correlated with the disposition and response to AZD6765iv may be analyzed.
- **Biomarker analysis**
 - Serum samples for optional exploratory biomarker analysis

Statistical methods

Efficacy analyses will be based on the modified intent-to-treat (mITT) analysis set that will include all randomized patients, who received at least 1 dose of IP and who have a baseline MADRS total score assessment and at least 1 post-baseline MADRS total score classified according to their randomized treatment.

Safety and tolerability assessments will be based on the safety analysis set, which will include all randomized patients who are given the IP, and for whom any post-dose data are available, classified according to the treatment actually received.

The primary efficacy variable, change from baseline to Week 6 in the MADRS total score, will be analyzed using a Mixed Model Repeated Measures (MMRM) analysis of all of the post-baseline MADRS total scores through the end of the study (Week 14). The model will include treatment, visit, treatment by visit interaction, and the baseline MADRS total score as fixed effects, and site as a random effect. Restricted Maximum Likelihood (REML) with an unstructured variance-covariance matrix will be used for estimation in the MMRM analysis. Each AZD6765iv dose will be compared with placebo.

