At Visit 1 and again before randomization at Visit 2, assessments will be conducted to ensure that the HAM-D-17 is ≥ 24 , CGI-S is ≥ 5 , and QIDS-SR-16 is ≥ 19 . The HAM-D-17 and a review of the patient’s prior antidepressant therapy will also be conducted prior to randomization and after medical clearance. If the patient does not meet the study entry criteria at Visit 2, the patient will be considered a screen failure and will not be randomized to the study. Patients who qualify will receive baseline clinical assessments of MADRS, HAM-A, S-STS, and CogState, and be randomly assigned in a 1:1:1 ratio to 1 of the 3 treatment arms:

- **Treatment A:** AZD6765iv 50 mg (AZD6765 Solution for Infusion, 0.5 mg/mL) by iv infusion
- **Treatment B:** AZD6765iv 100 mg (AZD6765 Solution for Infusion, 1.0 mg/mL) by iv infusion
- **Treatment C:** Placebo (0.9% sodium chloride [normal saline] solution for injection) by iv infusion

Patients will receive multiple infusions of AZD6765iv 50 mg or 100 mg, or placebo saline during the 12-week study treatment period and must be treated as outpatients during the entire course of the study. Patients will undergo the study procedures and assessments at designated visits per the study assessments (Table 4). Patients will be encouraged to eat and drink within 4 hours prior to infusion to reduce the risk of orthostatic hypotension.

The patient's depression and suicidality (suicide risk) will be assessed by the following instruments: Mini-International Neuropsychiatric Interview (MINI) (at screening), QIDS-SR-16, HAM-D-17 (screening and randomization only), MADRS, Columbia-Suicide Severity Rating Scale (C-SSRS), HAM-A, S-STS, CGI-S, and CGI-I. Dissociative symptoms will be assessed by Clinician Administered Dissociative States Scale (CADSS). The patient's quality of life will be assessed by the self-reported SDS. Cognitive functioning will be assessed using a battery of 4 tests of CogState ClinicalTrials (CogState, Ltd., New Haven, CT). A HAM-D-17 and a review of the patient's prior antidepressant treatment will be conducted after medical clearance and prior to randomization. After randomization, clinical measures to be conducted prior to infusion include QIDS, MADRS, HAM-A, S-STS, SDS, CGI-S, CGI-I and CogState. Measures to be collected after infusion include C-SSRS and CADSS.

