3.1.2 Randomization/double-blind treatment period (Weeks 1 to 12)

Patients will undergo all procedures and assessments at the designated visits per the study assessments ([Table 4](#)); visits are as follows:

Week 1: Visits 2, 3, and 4 (Days 1 to 7, Infusions 1 to 3)

Only qualified patients will be randomized (Visit 2, Day 1).

Patients will undergo the study procedures and assessments described for Day 1 (Visit 2) before randomization ([Table 4](#)). Assessments conducted before randomization will be considered baseline assessments. Qualified patients who meet the entry criteria including HAM-D-17 score ≥ 24 , CGI-S score ≥ 5 , and QIDS-SR-16 score ≥ 19 will be randomly assigned in a 1:1:1 ratio to 1 of the 3 treatment arms:

- **Treatment A:** Patients will receive AZD6765iv 50 mg (total dose) intravenously once per dosing day at the study site. The infusion will be a

final volume of 100 mL given at an infusion rate of 1.67 mL/min (0.833 mg/min) over 60 minutes.

- **Treatment B:** Patients will receive AZD6765iv 100 mg (total dose) intravenously once per dosing day at the study site. The infusion will be a final volume of 100 mL given at an infusion rate of 1.67 mL/min (1.667 mg/min) over 60 minutes.
- **Treatment C:** Patients will receive placebo (0.9% saline) intravenously once per dosing day at the study site. The infusion will be a final volume of 100 mL given at an infusion rate of 1.67 mL/min over 60 minutes.

During Week 1, all patients will receive 3 infusions on non-consecutive days. After Infusion 1 (Visit 2), patients will remain on site for at least 3 hrs after the end of infusion. Starting from Infusion 2 (Visit 3), patients will remain on site for at least 1 hr after the end of infusion. Prior to release from the site during every visit, patients must demonstrate stable vital signs and will be questioned about any AEs being experienced. To ensure safety, all patients must refrain from driving and operating heavy machinery for the remainder of the day after infusions 1, 2, and 3 (Week 1). Patients who are unaccompanied by a driver will be provided transportation to their home.

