6.2.1.2 Randomization visit (Visit 2)

Prior to the randomization visit, adequate documentation must be in place to confirm that the patient meets modified ATHF inclusion criteria of inadequate response to at least 2 previous antidepressant treatments of adequate dose and duration. In addition, results from all laboratory assessments conducted at the screening visit should be available and confirm that the patient continues to meet clinical and safety criteria for inclusion.

At the randomization visit, the QIDS-SR-16 will be administered first. Prior to conducting any further procedures, the QIDS-SR-16 should be scored (without review by the investigator) and if the inclusion criterion score of ≥ 19 is not met, no further study procedures are to be conducted and the patient will not be randomized. At no time may the patient be informed of the inclusion criterion score on the QIDS-SR-16. If the QIDS-SR-16 criterion is met, the HAM-D-17 interview will be conducted and the CGI-S will be completed to determine whether the patient meets the inclusion criteria of a HAM-D-17 total score ≥ 24 and CGI-S ≥ 5 . If these criteria are not met, no further procedures are to be conducted and the patient will not be randomized. If these criteria are met, the patient is randomized and the remaining clinical and laboratory assessments are conducted in accordance with Table 4.

The MADRS, CGI-S, S-STS, HAM-A, SDS, and Cogstate are conducted prior to the first infusion. After the first (and last) infusion, the patient must remain in the clinic for at least 3 hours after the infusion (T_4) during which time AEs are collected, and CADSS and C-SSRS are administered. Vital signs and orthostatic BP are measured at every infusion at multiple time points: T_0 , T_1 (vital signs only), and either at least 1 hour (T_2) after the end of infusion (all indicated visits, except for Visits 2 and 16), or, at least 3 hours (T_4) after the end of infusion (applies to Visits 2 and 16, which corresponds to first and last infusions).

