6.3.2 Instruments

The following is a description of all clinical rating instruments used to measure efficacy not described above in Section 6.2.2. All ratings will be made by the investigator or delegate, according to the schedule of events in Table 4. Patient-reported outcome scales include: QIDS-SR-16, SDS (efficacy), and S-STS, CADSS (safety).

To ensure consistency throughout the study, all site personnel (eg, physician, PhD, RN, or other healthcare professional skilled and experienced in the care of this patient population) administering the MADRS, HAM-D, C-SSRS, HAM-A, CADSS, CGI-I, and CGI-S, will receive training in conducting these assessments. In addition, certification will be required for MADRS, CGI, and C-SSRS scale administration (prior to rating these scales for this study). The back-up rater must meet the same qualifications as the primary rater and be authorized by the PI and approved by AstraZeneca or representative to conduct the ratings.

The scores in each of the scales will be recorded on the appropriate sections of the eCRF. Signs and symptoms revealed and recorded during the ratings should only be reported as AEs if they fulfill the criteria for an SAE or are the reason for discontinuation from treatment with the IP. Please see [Table 4](#) for the timing of evaluations.

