6.4.9.7 Clinician Administered Dissociative States Scale (CADSS)

The CADSS is a 23-item self-report scale (Bremner et al 1998). It is a reliable, valid self-report instrument designed to assess state symptoms of dissociation in response to a specified stressor. Severity of each dissociative symptom can range from 0 (not present) to 4 (extreme). The CADSS must be administered at designated visits after the infusion.

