11.1.5 CADSS

The CADSS total score will be calculated as the sum of the individual item scores. For CADSS, change from baseline to each assessment will be calculated as the visit score minus the baseline score.

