11.2.6.2 CADSS

The CADSS is a 23 item self-report scale ([Bremner et al 1998](#)). It is a reliable, valid self-report instrument. The severity of each dissociative symptom range from 0 (not present) to 4 (extreme). The change from baseline at each scheduled assessment in CADSS total score will be calculated.

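### The CADSS outcome is defined as change from baseline, but every CADSS is taken after an infusion, so the variable either cannot be computed or subtracts one post-infusion score from another

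*Protocol*

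**What the plan says.** **The outcome.** The safety outcome variables in the protocol synopsis list "Change in severity of dissociative symptoms at each scheduled assessment, as measured by change from baseline in the CADSS total scores". Section 11.1.5 gives the derivation: "For CADSS, change from baseline to each assessment will be calculated as the visit score minus the baseline score". Section 11.2.6.2 repeats it: "The change from baseline at each scheduled assessment in CADSS total score will be calculated". For the CADSS, the safety analysis in section 12.2.4 names only changes from baseline in the total score.

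**The timing.** Section 6.4.9.7: "The CADSS must be administered at designated visits after the infusion". Section 3.1: "Measures to be collected after infusion include C-SSRS and CADSS". Section 6.2.1.2 places the Visit 2 CADSS in the stay of at least 3 hours after the first infusion, "during which time AEs are collected, and CADSS and C-SSRS are administered". Section 6.3.1 lists it among the post-infusion ratings. Table 4 marks the CADSS at Visits 2 and 13, and footnote k puts it after the infusion. Nothing is marked at screening.

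**The baseline.** Section 3.1.2: "Assessments conducted before randomization will be considered baseline assessments". The CADSS is absent from the baseline assessments named in section 3.1 and from the measures that section 6.2.1.2 places before the first infusion.

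**The concern.** A change score is informative about an acute drug effect only if the subtracted value is free of drug. Here the only candidate for subtraction is a score taken after the first infusion. In the active arms it may already contain the dissociative effect that the scale is there to measure.

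The CADSS total is part of a stated safety objective (section 2.3). Section 1.4 describes ketamine's psychotomimetic effects within hours of infusion and presents a lower level of behavioral effects as a feature of AZD6765. A variable that shows no difference when the acute effect is stable, and an advantage for the drug when it wanes, could appear to support that profile whether or not it is true.

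**Working it through.** There is no stated figure to reproduce: the protocol gives no CADSS effect size, sample size or test. The check has two parts.

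**1. Is there a baseline?**

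- Required by section 3.1.2: an assessment before randomization.
- Available from Table 4 with footnote k: post-infusion Visit 2 (infusion 1) and post-infusion Visit 13 (infusion 12, Week 6).
- Result: none qualifies. Even if baseline is read more loosely as anything before the first infusion, none qualifies.
- Contrast: section 6.4.7.1 gives the ECG an explicit baseline at the pre-infusion time point of Visit 2. The CADSS has no such rule.

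Read strictly, the named variable cannot be calculated.

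**2. What would the change show if the Visit 2 score were used as baseline?** The protocol does not state this rule. It is the only substitution that the Table 4 schedule allows.

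Inputs, all assumed:
- P2 and P13: mean placebo CADSS after infusions 1 and 12.
- D: acute drug effect on the mean score after infusion 1.
- r: share of D present after infusion 12.

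Formulas:
- Mean change on placebo: P13 - P2.
- Mean change on drug: (P13 + rD) - (P2 + D).
- Difference in change, drug minus placebo: rD - D = (r - 1)D.
- Difference in raw totals, drug minus placebo: D at Visit 2 and rD at Visit 13.

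| D | r | Difference in change, (r - 1)D | Raw difference, Visit 2 | Raw difference, Visit 13 |
|---|---|---|---|---|
| 2 | 1 | 0 | 2 | 2 |
| 2 | 0.5 | -1.0 | 2 | 1.0 |
| 5 | 1 | 0 | 5 | 5 |
| 5 | 0.75 | -1.25 | 5 | 3.75 |
| 5 | 0.5 | -2.5 | 5 | 2.5 |
| 5 | 0 | -5 | 5 | 0 |
| 10 | 1 | 0 | 10 | 10 |
| 10 | 0.5 | -5.0 | 10 | 5.0 |

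If the effect grows, for example r = 1.5 with D = 5, the difference in change is (1.5 - 1) x 5 = +2.5, against a raw Visit 13 difference of 1.5 x 5 = 7.5. Only the increment shows.

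In every row the first-dose effect enters the change only as a quantity subtracted. It never shows as an excess on drug. The raw comparison shows it directly at Visit 2.

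The same algebra applies to any further post-infusion CADSS, with r taken as the share present at that infusion. It therefore does not depend on settling which later visits carry the scale.

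**The case against.** **The information is not lost.** The safety objective refers to CADSS total scores, section 12.2 says that safety variables will in general be summarized descriptively with individual data listed, and randomization makes the raw post-infusion totals comparable between arms. All of this stands, and it is why the repair is cheap. It does not make the named outcome right. Section 12.2.4 promises both raw values and changes for laboratory tests, vital signs, ECG, weight and BMI, but for the CADSS it names changes only.

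**The statistical analysis plan can settle it.** A plan, not shown here, could add raw-score summaries. It could not supply a pre-infusion score that the schedule does not collect. The conflict between derivation and schedule lies within the protocol.

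**Cancellation is conditional.** A reader might infer that the planned analysis is bound to cancel the dissociative effect. The documents do not support that. Under the section 3.1.2 definition nothing is computed, so nothing cancels. Exact cancellation needs two assumptions that the protocol does not state: the post-infusion Visit 2 score as baseline, and the same effect at infusions 1 and 12.

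**Adverse event reporting.** A reader might also infer that dissociation would escape the safety data altogether. That goes too far. Section 6.3.2 does restrict what is reported from scales: "Signs and symptoms revealed and recorded during the ratings should only be reported as AEs if they fulfill the criteria for an SAE", with a further exception for findings that lead to discontinuation of the investigational product. But section 6.4.3 still records events that are volunteered, given in answer to the open question, or observed, and Table 4 footnote l has patients asked about adverse events before leaving each infusion visit. Adverse event reporting is a partial backup.

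**Importance.** Section 1.1.2.1 reports few dissociative events with this drug in MDD, and section 1.4 reports none after a single 100 mg infusion in 16 patients. The CADSS carries no hypothesis test or alpha.

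**Conclusion.** The point holds as a mismatch between the named CADSS outcome and the schedule. On the protocol's own baseline definition the variable cannot be calculated. With the post-infusion Visit 2 score as a substitute baseline, the expected drug-placebo difference is (r - 1)D: zero for a stable effect, negative for a waning one, and only the increment for a growing one.

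The absence of a baseline rests on the text alone. The size rests on assumed D and r, because the protocol gives no CADSS figures.

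This should be fixed, but it is not critical: one descriptive safety scale is affected, the primary and key secondary analyses are untouched, and the data needed for a valid comparison are already collected.

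**What to change.** - **Analysis wording (no new data).** In the synopsis and sections 11.1.5, 11.2.6.2 and 12.2.4, replace change from baseline with a between-arm summary of the raw post-infusion CADSS total at each scheduled CADSS visit: means by arm and the proportion of patients scoring above 0. Cost: wording only.
- **If change is to be kept.** It needs a pre-infusion CADSS, at screening or before the first infusion at Visit 2, named as the baseline. That changes the assessment schedule and may need an approved amendment (section 8.5). It may also be unobtainable for patients already treated: section 3.1.3 provides for patients who completed their infusions before Amendment 2 was implemented.
- **Reconcile the schedule text.** Section 6.2.1.2 implies a CADSS after the last infusion as well as the first. The Weeks 2 and 3 and Weeks 7 through 12 paragraphs of section 3.1.2 also mention a post-infusion CADSS, while Table 4 marks only Visits 2 and 13. The passages must be made to agree so that the visits to be summarized are fixed. Cost: wording only, unless visits are added.

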11.2 Calculation or derivation of safety variables

A treatment-emergent AE (TEAE) is defined as any AE that started on or after the first dose of IP up to 30 days after the last dose of IP. An AE already present at the time of the first dose of IP that worsens in intensity following exposure to IP or an AE with an unknown/not reported onset date will also be considered as treatment emergent.

11.2.1 Other significant adverse events (OAE)

During the evaluation of the AE data, AstraZeneca or representative will review the list of AEs that were not reported as SAEs and discontinuations due to adverse events (DAEs). Based on the expert's judgment, significant AEs of particular clinical importance may, after consultation with the Global Patient Safety Physician, be considered OAEs and reported as such in the CSR. A similar review of laboratory, vital signs, and ECG data will be performed for identification of OAEs.

Examples of these are marked hematological and other laboratory abnormalities, and certain events that lead to intervention (other than those already classified as serious), dose reduction or significant additional treatment.

11.2.2 Laboratory safety assessments

Change from baseline at each visit will be calculated as the visit value minus the baseline value for each continuous clinical chemistry, hematology, and urinalysis measurement.

11.2.3 Weight and BMI

A screening and baseline BMI will be calculated. Change from baseline to Week 14 will be calculated as the Week 14 value minus the baseline value. Also, the proportions of patients who have a weight gain $\geq 7\%$ compared with baseline will be tabulated.

11.2.4 ECG

Change from baseline at each visit will be calculated as the visit value minus the baseline value for each ECG parameter: heart rate, QRS duration, PR interval, RR interval, QT and calculated QTcF interval.

11.2.5 Vital signs

Change from baseline at each visit will be calculated as the visit value minus the baseline value for each vital sign: BP, pulse rate (supine and standing), and oral temperature.

11.2.6 Other safety assessments

11.2.6.1 C-SSRS

Occurrence of suicidal behavior after baseline up to Week 3 will be defined as having answered “yes” to at least 1 of the 4 suicidal behavior subcategories (actual attempt, interrupted attempt, aborted attempt, and preparatory acts or behavior) at any post-baseline evaluation.

Occurrence of suicidal ideation after baseline up to Week 3 will be defined as having answered “yes” to at least 1 of the 5 suicidal ideation subcategories (wish to be dead, non-specific active suicidal thoughts, active suicidal ideation with any methods [no plan] without intent to act, active suicidal ideation with some intent to act [without specific plan], and active suicidal ideation with specific plan and intent) at any post-baseline evaluation.

